#### 7.2.2.4 Week 46/End-of-Treatment (EOT) or Early Termination Procedures

- Physical/ neurological exam
- PML checklist
- Urine pregnancy test (females only, not diagnosed as postmenopausal)
- CBC with differential and platelets
- Ophthalmoscopy with OCT (where available) and retinal photos
- Clinical laboratory tests (serum chemistry, hematology, coagulation parameters, urinalysis and CRP)
- Pulmonary function test (spirometry)
- Stool Sample

- Fecal calprotectin
- Flexible proctosigmoidoscopy
- [REDACTED]
- [REDACTED]
- Diary review
- [REDACTED]
- Vital signs
- [REDACTED]
- 12-lead ECG
- Drug administration
- Drug accountability
- Record adverse events
- Record concomitant medications/procedures

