## 9.3 Analysis Populations

The analyses of all proportion based efficacy variables will use the Intent-to-Treat (ITT) population as primary. For other continuous efficacy endpoints, the Modified Intent-to-Treat (MITT) population will be used as primary. A completer's population will be used as a secondary analysis population for the efficacy endpoints.

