### 9.6.1 Data Analysis for Secondary Efficacy Endpoints

The secondary efficacy outcome of achievement or maintenance of clinical response will be based on the proportion of patients who achieve or maintain clinical response [defined as a decrease in 3-component Mayo Clinic score of  $\geq 2$  points and at least 30% with either a decrease of rectal bleeding of  $\geq 1$  or rectal bleeding score of 0 or 1] at Week 46 compared to APD334-003 baseline using the ITT population. All patients who prematurely discontinue for any reason will be considered failures (non-responders) for all the proportion based endpoints. Similar analyses will be performed in terms of the other Week 46 proportion based endpoints such as proportion of patients achieving clinical remission and proportion of patients with endoscopic improvement.

For each study visit during the study, stool frequency and rectal bleeding subscores will be derived

- [Redacted bullet point]
- [Redacted bullet point]
- [Redacted bullet point]

All patients who prematurely discontinue for any reason will be considered failures (non-responders) for all the proportion based endpoints.

Descriptive statistics of N, mean or mean change, and standard deviation will be produced for continuous efficacy endpoints.

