## 4. GENERAL STATISTICAL CONSIDERATIONS

Continuous data will be summarized using descriptive statistics (i.e., n, mean, median, standard deviation (SD), 90% confidence interval (CI) for change or percent change from baseline, minimum and maximum). For the summary statistics of all numerical variables unless otherwise specified, minimum and maximum will be displayed to the same level of precision as reported. Mean, median and 90% CIs will be displayed to one level of precision greater than the data collected. Standard deviation will be displayed to two levels of precision greater than the data collected.

For proportion-based measures, n, frequencies, proportion and its 90% CI will be produced. The denominator for all percentages will be the number of patients within the treatment group for the analysis set of interest, unless otherwise stated. Percentages will be presented to 1 decimal place. When count data are presented, the percentage will be suppressed when the count is zero in order to draw attention to the non-zero counts. A row denoted “Missing” will be included in count tabulations where specified on the shells to account for dropouts and missing values.

There is no formal between group inferential comparisons for study endpoints due to lack of control group. Summary statistics will be provided for the primary safety endpoint, secondary efficacy endpoints, exploratory efficacy endpoints, and additional safety measures. All analysis summaries will be presented as follows:

Previously Treated in APD334-003 (APD334-005 treatment: 2 mg etrasimod)				APD334-005 treatment:	APD334-005 treatment:
Placebo	1 mg etrasimod	2 mg etrasimod	1 mg & 2 mg etrasimod	2 mg etrasimod	Placebo

[figure not shown]
[figure not shown]
Listings will include a subtitle to indicate both treatments, i.e. treatment received in APD334-003 study and treatment received in APD334-005 study.

[figure not shown]
[figure not shown]
[figure not shown]
If endoscopy was performed prior to Week 46, then last observation carried forward (LOCF) imputation method will be used for the endoscopy subscore. Any endoscopy performed during the APD334-005 extension study (after Week 12 visit) will be used for LOCF imputation.

All data summaries and statistical analyses will be performed using the SAS software version 9.3 or higher (SAS Institute, Cary, NC).

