## **4.4. Analysis Populations**

The analyses of all proportion-based and all continuous efficacy variables will use the Modified Intent-to-Treat (MITT) population as primary. In addition, all endpoints that include the endoscopy subscore will use Completers population (CP).

Analysis populations will be presented in a listing for all enrolled patients.

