## **8.3. Secondary Efficacy Analysis**

Secondary efficacy endpoints are listed in Section [3.2.2](#).

[figure not shown]
The secondary efficacy outcome of achievement or maintenance of clinical response will be based on the proportion of patients who achieve or maintain clinical response at end of treatment compared to APD334-003 baseline using the MITT and CP populations. Summary statistics i.e. total number of patients (N), frequencies (n), proportion (%) and its 90% CI for patients that achieved or maintained clinical response (responders) at end of treatment in APD334-005 will be produced as described in Section [4](#).

[figure not shown]
Similar summary statistical analyses will be produced for the second secondary efficacy outcome i.e. clinical remission at Week 46 compared to APD334-003 baseline.

Each secondary efficacy endpoint will be summarized, within the same presentation, by the following:

- Proportion of patients that achieved clinical response/clinical remission at Week 12 in APD334-003
- Proportion of patients that achieved clinical response/clinical remission at end of treatment in APD334-005
- Proportion of patients that achieved clinical response/clinical remission at both Week 12 in APD334-003 and end of treatment in APD334-005

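### No visible SAP text keeps the protocol's rule that early discontinuers are non-responders, so a discontinuer with an early endoscopy can be counted as a secondary-endpoint success

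*SAP*

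**What the plan says.** Protocol 9.6.1 sets the rule for early stopping, and gives it twice: "All patients who prematurely discontinue for any reason will be considered failures (non-responders) for all the proportion based endpoints". Protocol 9.3 names the patient set: "The analyses of all proportion based efficacy variables will use the Intent-to-Treat (ITT) population as primary".

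SAP 4 sets a different rule for one component of the score: "If endoscopy was performed prior to Week 46, then last observation carried forward (LOCF) imputation method will be used for the endoscopy subscore". It then says which examinations qualify: "Any endoscopy performed during the APD334-005 extension study (after Week 12 visit) will be used for LOCF imputation". It gives no minimum time on treatment and no exclusion for patients who stopped.

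On the patient set, SAP 4.4 says: "The analyses of all proportion-based and all continuous efficacy variables will use the Modified Intent-to-Treat (MITT) population as primary". MITT entry needs a baseline and a measurement in the extension for the endpoint concerned (SAP 4.4.1). The Completers population imputes nothing and leaves out patients who did not complete (SAP 4.4.2).

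The SAP gives two time points. SAP 3.2.2 and 8.3 mostly assess the endpoints at end of treatment, but both also refer to Week 46, as in "clinical remission at Week 46 compared to APD334-003 baseline".

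An early endoscopy in a discontinuer is a planned event. Protocol 7.2.2.4 is one list for both situations, "Week 46/End-of-Treatment (EOT) or Early Termination Procedures", and it contains "Flexible proctosigmoidoscopy" and a diary review.

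**The concern.** The secondary objective is to achieve and maintain response or remission after 46 weeks of treatment. A patient who stopped early has not shown that, and the protocol's rule reflects this by scoring every such patient as a failure.

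Under the visible SAP, the same patient can enter MITT through the early-termination endoscopy and have that value stand as the final endoscopy component. If the other two components qualify, the patient is a success. If the patient also responded at Week 12 of APD334-003, he or she enters the SAP 8.3 row for success at both times, which is the maintenance result.

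This would treat a value obtained at stopping as if it had been sustained to Week 46. The change is also not visible as a change: the readable part of SAP 12 lists the 90% intervals, both revised definitions, the removal of ITT and the new Completers definition. It lists neither LOCF nor the loss of the failure rule.

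**Working it through.** The documents give no sample size, dropout rate or response rate, so there is no planned figure to reproduce. The check is a reading of the rules, followed by an illustration on assumed inputs.

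**Reading the rules for a discontinuer with an early-termination endoscopy**

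1. Protocol 9.6.1: failure, whatever the scores.
2. SAP 4, with the endpoint read at Week 46: the endoscopy subscore is carried forward.
3. SAP 3.2.2 and 8.3, with the endpoint read at end of treatment: the early-termination endoscopy is simply the observed final value, and LOCF is not needed.
4. On either SAP reading, the outcome then depends on the stool frequency and rectal bleeding scores. No visible text makes the patient a failure.
5. Completers: the patient is left out, neither success nor failure.

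So no visible SAP analysis produces the protocol's estimate.

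**Illustration.** All inputs are assumptions:
- d = share who stop early (10–30%; middle case 20%)
- e = share of discontinuers with an extension endoscopy (50–100%; 80%)
- rd = share of those who meet all criteria (0–40%; 20%)
- rc = success rate in completers (40–75%; 60%)

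All completers are taken to have an endoscopy.

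| Analysis | Formula | Middle case |
|---|---|---|
| Protocol rule, all treated | (1−d)·rc | 0.80 × 0.60 = 48.0% |
| Discontinuers can succeed, all treated | (1−d)·rc + d·e·rd | 0.480 + 0.20 × 0.80 × 0.20 = 51.2% |
| Discontinuers fail, MITT | (1−d)·rc / [(1−d) + d·e] | 0.480 / 0.96 = 50.0% |
| Visible SAP, MITT | [(1−d)·rc + d·e·rd] / [(1−d) + d·e] | 0.512 / 0.96 = 53.3% |
| Completers | rc | 60.0% |

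The effect of this point alone, with the patient set held fixed, is 51.2 − 48.0 = 3.2 points over all treated patients, or 53.3 − 50.0 = 3.3 points within MITT. The other 2.0 points of the 5.3-point gap between 48.0% and 53.3% come from the smaller MITT denominator. That is a separate change, which SAP 12 declares.

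Over the assumed ranges the effect over all treated patients is d·e·rd. The minimum is 0, when rd = 0. The maximum is 0.30 × 1.00 × 0.40 = 12.0 points. With e = 1 no discontinuer drops out of MITT, so the maximum within MITT is also 12.0.

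The largest total gap between the visible SAP and the protocol rule is 16.3 points (rc 75%, d 30%, e 50%, rd 40%: 0.585 / 0.85 = 68.8% against 0.70 × 0.75 = 52.5%). Of this, 0.525 / 0.85 − 0.525 = 9.3 points come from the denominator and 0.060 / 0.85 = 7.1 points from discontinuers counted as successes (rounded).

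**The case against.** - **Text is missing where a rule might sit.** Figures are absent beside the LOCF text in SAP 4 and in SAP 8.3, and parts of SAP 12 are redacted. Carrying one subscore forward can coexist with a rule that discontinuers fail. This stands: the evidence shows only that no visible text keeps the rule. If a surviving rule exists, the sponsor need only confirm that it overrides LOCF.
- **LOCF covers endoscopy alone.** A reader might infer that discontinuers with a good endoscopy will be counted as successes. The documents do not support that. The derivation of the diary scores is redacted in Protocol 9.6.1, and the day ranges of SAP 4.1 are not shown. A patient without usable diary scores would stay in the denominator under SAP 4 and not be a success. The supported statement is that such a patient can be counted.
- **LOCF may not be the operative step.** On the end-of-treatment reading nothing is carried forward. This is right, but it leads to the same result by another route, so limiting LOCF without restating the failure rule would not close the gap.
- **Not every endoscopy before Week 46 is an early termination.** A reader might infer that most are. The endoscopy timing is partly redacted in Protocol 6.9.1 and SAP 8.1.1, and Protocol 6.14 sets no visit windows. A completer's final endoscopy may fall before nominal Week 46. LOCF for that patient is reasonable, and Protocol 9.6.1 does not call that patient a failure.
- **The consequences are limited.** The primary endpoint is safety. The efficacy endpoints carry no hypothesis test. A Completers analysis is planned, substantial differences from MITT are to be investigated, and discontinuations are tabulated by reason. This lowers the severity. It does not restore the protocol's estimate, because Completers removes discontinuers rather than failing them.

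**Conclusion.** The point holds as a conflict between Protocol 9.6.1 and the visible SAP, not declared in the visible SAP 12. For discontinuers within a fixed patient set, its effect on the response, remission and maintenance proportions cannot be negative, because the protocol already scores every one of them as a failure.

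The size is unknown. On the assumed ranges it is 0 to about 12 points, and zero is possible. Two stronger readings should be avoided. The documents give no basis for a lower bound above zero. The 16.3-point gap should not be attributed to this point, since much of it comes from the declared move from ITT to MITT.

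Severity is moderate. No type I error is at stake, but these are the study's named secondary efficacy results, and their point estimates and intervals are what will be reported.

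**What to change.** 1. In SAP 4 and 8.3, state that a patient who discontinued before the planned final visit is a non-responder for clinical response and remission, even if an earlier extension endoscopy exists. Referring to the planned final visit also suits patients enrolled under Amendment 02, whose final assessments were at Week 52 (SAP 3.1).
2. In the main analysis, keep endoscopy LOCF only for patients who completed treatment, for example where the final endoscopy fell before nominal Week 46. Moving all LOCF to a sensitivity analysis would go too far, because it would also affect these completers.
3. Show LOCF for discontinuers only as a sensitivity row, with the number of carried values and the study week each came from.
4. List any remaining departure from Protocol 9.6.1 in SAP 12, with the reason.

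The cost is SAP wording and one flag from the disposition data. No new data are needed. The reported rates may be slightly lower.

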#### **4.1. Time points and Day Ranges**

Since it is not always possible for all study participants to come in for their clinic visits on the exact day specified in the protocol schedule, the ‘Week’ of a patients visit will be defined by the following relative day ranges.

## **4.2. Sample Size**

Patient enrollment is limited by the number of patients who complete the APD334-003 study. Therefore, sample size calculation is not needed.

## **4.3. Randomization, Stratification, and Blinding**

### **4.3.1. Randomization and Stratification**

Not applicable for this open-label extension study.

Note: Patients that were enrolled under Protocol Amendment 02 (28 Sep 2015) were randomized to Placebo or 2 mg q.d. etrasimod and remained blinded. More details about changes in the study design are covered in Sections [1](#) and [12](#).

### **4.3.2. Blinding**

The extension study is an open-label study, however in order to keep the blind of the induction study intact, the sponsor, patients, and personnel involved with the conduct of the APD334-005 study will continue to be blinded to the total white blood cell (WBC) and lymphocyte counts, as access to this information may lead to unintentional unblinding of a patient (due to Investigational Product's mechanism of action). A central contract research organization (CRO) physician(s) unblinded to the leucocyte count will continue to review and monitor the total WBC and lymphocyte counts for safety purposes in the trial. The study site personnel will not receive laboratory results for the total WBC or lymphocyte counts. Further details are included in the Covance Labs Data Transfer Specifications ([COVANCE 2018](#)).

## **4.4. Analysis Populations**

The analyses of all proportion-based and all continuous efficacy variables will use the Modified Intent-to-Treat (MITT) population as primary. In addition, all endpoints that include the endoscopy subscore will use Completers population (CP).

Analysis populations will be presented in a listing for all enrolled patients.

### **4.4.1. Modified Intent-To-Treat Population (MITT)**

This MITT population consists of all patients, who received at least 1 dose of etrasimod or Placebo, have a baseline measurement, and have a post-enrollment measurement in the extension study for the specific efficacy endpoint being assessed. Note that MITT population can vary with endpoints since some patients may have the needed data for inclusion in the MITT population for some endpoints but not for others.

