### **4.4.2. Completers Population (CP)**

This CP population consists of all patients in the MITT population who completed the extension study based on the study completion status collected on the End of Study CRF page. No missing data will be imputed for this analysis. Any substantial differences between conclusions based on the MITT population and the CP population will be investigated. Note that CP population will be used only for endpoints that include the endoscopy subscore, unless otherwise stated.

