The clinical remission definition has been updated to include “a rectal bleeding score of 0 or 1” in comparison with Protocol Amendment 04 (27 Mar 2017) to be consistent with the definition in final SAP of APD334-003 study.

The clinical response definition has been updated as “a patient has achieved clinical response if he/she meets criteria of clinical remission, or meet criteria of clinical response defined in the protocol.” to be consistent with the definition in final SAP of APD334-003 study.

The following changes have been applied to the Analysis Populations to the SAP in comparison with Protocol Amendment 04 (27 Mar 2017):

- ITT population has been removed – no longer needed as APD334-005 is an open label study
- Definition of CP population has been updated to include “This CP population consists of all patients in the MITT population who completed the extension study” and “Note that CP population will be used only for endpoints that include the endoscopy subscore, unless otherwise stated.” – to be consistent with the definition in final SAP of APD334-003 study
- CP population will be used only for endpoints that include the endoscopy subscore:

[REDACTED]

Sponsor was notified that laboratory tests for five patients [REDACTED] had been sent to local labs for the purpose of safety follow up on blood cell counts after last treatment. Such follow up may still be needed at time of database lock. The local laboratory results will be translated in English and archived in study file. Sponsor will write a section in CSR to describe the findings and to assess the safety issues for these [REDACTED] patients.

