## 14.2. Listing of Efficacy Parameters and Study Populations Analysed

[figure not shown]
Efficacy Parameters	Response Analysed	Study Populations Analysed
Secondary Endpoints		
Clinical Response	Proportion	MITT, CP
Clinical Remission	Proportion	MITT, CP
Exploratory Endpoints		

[figure not shown]

[figure not shown]

[figure not shown]

[figure not shown]

[figure not shown]

[figure not shown]

[figure not shown]

[figure not shown]

This is a representation of an electronic record that was signed electronically, and this page is the manifestation of the electronic signature.

---

UserName: [REDACTED]  
Title: [REDACTED], Biostatistics  
Date: Tuesday, 27 November 2018, 02:20 PM Pacific Daylight Time  
Meaning: Author Approval  
=====

UserName: [REDACTED]  
Title: [REDACTED], Biostatistics & Data Management  
Date: Tuesday, 27 November 2018, 02:23 PM Pacific Daylight Time  
Meaning: Approval  
=====

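### The SAP drops the protocol's all-dosed set for response and remission; on the natural reading, patients who discontinue without an extension endoscopy leave the denominator, and the end-of-treatment rates can then only rise or stay level

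*SAP*

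**What the plan says.** Protocol 9.3 makes the intent-to-treat (ITT) set primary for every proportion-based efficacy variable. That set is all enrolled patients dosed with APD334 in the extension; no post-baseline measurement is required. Protocol 9.6.1 adds that anyone who stops early, for whatever reason, is a non-responder.

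SAP 4.4 replaces this: "The analyses of all proportion-based and all continuous efficacy variables will use the Modified Intent-to-Treat (MITT) population as primary". To be in MITT for a given endpoint, a dosed patient must also "have a baseline measurement, and have a post-enrollment measurement in the extension study for the specific efficacy endpoint being assessed" (SAP 4.4.1). The only other efficacy set is nested in it: "This CP population consists of all patients in the MITT population who completed the extension study" (SAP 4.4.2). SAP 8.3 assesses response "at end of treatment compared to APD334-003 baseline using the MITT and CP populations" and treats remission similarly. The Appendix 14.2 table, "Listing of Efficacy Parameters and Study Populations Analysed", shows MITT and CP (the completers population), and nothing else, against both endpoints.

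Two rules in SAP 4 matter here. On percentages: "The denominator for all percentages will be the number of patients within the treatment group for the analysis set of interest, unless otherwise stated". On carrying endoscopy forward: "Any endoscopy performed during the APD334-005 extension study (after Week 12 visit) will be used for LOCF imputation".

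SAP 12 gives the reason for removing ITT: it is "no longer needed as APD334-005 is an open label study".

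**The concern.** The stated reason does not meet the point. Whether a study is blinded has no bearing on whether patients leave it. Protocol Amendment 04, on which the SAP is based, was already single-arm and open label (protocol 3.1 and 5.5), and it kept ITT together with the failure rule.

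Both endpoints use the 3-component Mayo score, which includes the endoscopy subscore. If an extension endoscopy is needed to have a measurement of the endpoint, a patient who discontinues without one is a failure under the protocol but absent under the SAP. CP cannot bring that patient back because it lies inside MITT. Last observation carried forward (LOCF) cannot either, because the Week 12 endoscopy is not a permitted source.

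With no control group and no hypothesis test, the reported proportion and its interval are the efficacy result. An error that can run only in the favourable direction therefore deserves attention, even for a secondary endpoint.

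**Working it through.** The documents give no sample size, dropout rate, expected response rate or share of discontinuers scoped at exit, so there is no stated figure to reproduce. The check is denominator arithmetic.

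**Direction.** Let N be the dosed patients, x the responders at end of treatment, and m the patients who discontinue without an extension endoscopy. Under protocol 9.6.1 none of the m is in x.

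- Protocol rule: x / N
- SAP MITT, natural reading: x / (N − m)

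Since N − m ≤ N, the MITT rate is never below the protocol-rule rate. Enumerating every N from 1 to 150 with every feasible m and x gave no exception. The same holds for the SAP 8.3 row counting patients who meet the criterion at both Week 12 and end of treatment, because that row also requires success at end of treatment.

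**Where the direction fails.** The Week 12 row in SAP 8.3 can move either way, because an excluded patient may have been a Week 12 responder. Assume N = 100, 60 Week 12 responders and 10 excluded. The all-dosed figure is 60/100 = 60.0%. If all ten excluded were responders, the row shows (60 − 10)/90 = 55.6%; if none were, 60/90 = 66.7%.

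**Size, under assumptions.** Assume N = 100 patients on 2 mg, d discontinuing, response p among completers (all with complete data), a share e of discontinuers with an extension endoscopy, and every discontinuer counted as a failure under both rules.

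- Protocol rule: p(N − d) / N
- SAP MITT: p(N − d) / [(N − d) + d·e]

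Example: p = 0.6 and d = 20 give 0.6 × 80 = 48 responders. Protocol rule: 48/100 = 48.0%. MITT with e = 0.8: 48/(80 + 16) = 48/96 = 50.0%.

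Excess of MITT over the protocol rule, in percentage points:

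| p | d | Protocol rule | e = 1 | e = 0.9 | e = 0.8 | e = 0.5 | e = 0 |
|---|---|---|---|---|---|---|---|
| 60% | 10 | 54.0% | 0 | 0.5 | 1.1 | 2.8 | 6 |
| 60% | 20 | 48.0% | 0 | 1.0 | 2.0 | 5.3 | 12 |
| 60% | 30 | 42.0% | 0 | 1.3 | 2.7 | 7.4 | 18 |
| 40% | 10 | 36.0% | 0 | 0.4 | 0.7 | 1.9 | 4 |
| 40% | 20 | 32.0% | 0 | 0.7 | 1.3 | 3.6 | 8 |
| 40% | 30 | 28.0% | 0 | 0.9 | 1.8 | 4.9 | 12 |

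**Intervals.** The SAP specifies 90% intervals, and its visible text names no method. For p = 0.6 and d = 20:

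| Estimate | Exact (Clopper-Pearson) | Wilson |
|---|---|---|
| 48/100 (protocol rule) | 39.4–56.7% | 39.9–56.2% |
| 48/96 (e = 0.8) | 41.2–58.8% | 41.7–58.3% |
| 48/90 (e = 0.5) | 44.1–62.4% | 44.7–61.8% |
| 48/80 (e = 0) | 50.2–69.2% | 50.8–68.5% |

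**The case against.** **The reading of MITT is not settled.** SAP 4.4.1 does not mention endoscopy. Two of the three score components come from a daily diary (SAP 8.1.4), which might count as a measurement. SAP 4 also allows a row for missing values where the table shells call for it, and the shells are not shown. If diary data admit every discontinuer and the failure rule applies, the excess is zero. This stands as a limit, and is itself a reason to state the entry rule.

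**Some text cannot be seen.** Parts of SAP 4 and 8.3, all of SAP 8.5, and bullets in protocol 9.6.1 are not visible and may hold missing-data rules. One can say only that no all-dosed analysis is visible. The removal of ITT in SAP 12 and the two sets named in Appendix 14.2 are visible, however.

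**Few patients may be lost, and they can be traced.** Endoscopy is an early-termination procedure (protocol 7.2.2.4), and sites are to make every effort to complete such procedures (protocol 6.13.1). That makes the e = 0 column an extreme, but does not fix the number lost. SAP 4.4 lists population membership for all enrolled patients. If completers have complete data, a reader could approximate the protocol rate as CP responders over the Safety count for the 2 mg group, but no visible output reports it.

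**The stakes are modest.** Efficacy is secondary and descriptive, and the change is disclosed in a SAP finalised before database lock. Both are correct.

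Three stronger inferences are tempting, and the documents do not support them:

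- A reader might infer that the SAP has abandoned the failure rule and will score discontinuers by LOCF. The rule is not repeated in the visible SAP, but its removal is not among the visible changes in SAP 12 either. Its status within MITT cannot be determined.
- A reader might infer that every reported rate is pushed upward. The Week 12 row is not, and for completers without an endoscopy no rule is visible, so the direction is not established for them.
- A reader might infer that the excluded patients vanish from the study. They remain in the safety and disposition summaries and may enter MITT for endpoints without endoscopy.

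**Conclusion.** The point holds in a limited form and should be fixed. The SAP replaces an all-dosed denominator for clinical response and remission with one that depends on having endpoint data, and its stated reason does not cover attrition. The favourable direction rests on three conditions: MITT membership requires an extension endoscopy, endpoint definitions are held fixed (SAP 12 changes them separately), and excluded discontinuers count as failures. It then applies to the end-of-treatment and both-timepoints rates.

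The size in this trial is unknown. Under the assumptions tabulated, the excess is 0.4 to 2.7 points if 80% to 90% of discontinuers are scoped and 1.9 to 7.4 points if half are. These are illustrations, not bounds on the SAP as written, because they assume the failure rule still applies within MITT. The primary safety analysis is unaffected.

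**What to change.** - For patients given 2 mg etrasimod in APD334-005, report end-of-treatment response and remission, and the both-timepoints rows, with all dosed patients as the denominator and early discontinuation as non-response, as in protocol 9.6.1.
- Show the Amendment 02 placebo patients in their own column on the same basis.
- Keep MITT with endoscopy LOCF, and CP, as labelled sensitivity analyses. Report for each endpoint how many dosed patients MITT excludes.
- State in SAP 4.4.1 whether an extension endoscopy is required for MITT membership for these two endpoints or whether diary subscores suffice.
- Confirm that the failure rule applies, and record any change to it in SAP 12.
- Optionally, and beyond the visible protocol rule, count completers without an evaluable score as non-responders.

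The cost is some SAP wording and one more set of table columns, with no new data. The downside is that the headline rates may be lower.
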